[phcon_rescue_bronch] 8. During the present cold/flare-up, was the rescue bronchodilator (ventolin, bricanyl) - blue inhaler used at home?

- 1 Yes
0 No

If according to the parent(s)/guardian(s), has the child had a cold, since the last contact?
(phcon_cold_lascon == Yes)

[phcon_rescue_bronch_2] 8. During the present or past cold/flare-up, was the rescue bronchodilator (ventolin, bricanyl) - blue inhaler used at home?

- 1 Yes
0 No

[phcon_rescue_bronch_dur] 8.1 Total duration of β 2-agonist use (Days):

- **REDCap3 database - written parental report: Duration of β 2-agonist use defined as the number of days with of β 2-agonist use**, obtained from the REDCap3 database, parental diary:

A valid diary set was defined as least 2 or more consecutive days with valid reporting of B2-agonist use, with no more than one missing day of recording between the first and last day of reporting. If a daily value is missing between the first and the last day of bronchodilator use, the score will be imputed using the last score carried forward.

- Q: Has your child taken Ventolin (or blue inhaler) (salbutamol, Bricanyl®, terbutaline but NOT Zenhale)? **[adyc_blue_inh]**
- Q: Which? **[adyc_blue_inh_choice]**
 - 1 : Ventolin® ou salbutamol
 - 2 : Bricanyl® ou terbutaline
- Q: If Yes, and No. puffs (or nebulles) / 24hrs **[adyc_blue_inh_ify]** is not missing
 - If 1. ventolin, then dose =number of puffs x 1
 - If 2. bricanyl , then dose = number of puffs x2
 - If number of puffs missing, impute from previous day.

Duration is the time elapsed between the first and last day with rescue B2-agonists

Number of lost parental workdays and productivity

The impact of flare-ups on the number of lost parental workdays as documented through verbal and written parent reports. This will be summarized as the total number of days that a parent reports that he/she missed work due to a cold or asthma flare up or to take care of his/her child related to an asthma flare up. Only one parent is surveyed for each flare-up. Reports will be collected from the verbal and written parent CRFs as follows:

Verbal parental report

REDCap, CRF Visit and Phone contact (Section 7):

- From Q 7. Since the last contact, has any of the child's parents or guardians missed work due to the child's cold or asthma flare-up?
- Up to Q 7.1.1 and 7.2.1 and 7.3.1 etc.

Written parental report

REDCap3, CRF Effects of a Young Child's Cold or Asthma Flare-up on Parents(ECAP), completed by parents after each exacerbation.

- Q 23. How many days of work or regular planned activities did you miss because you had to take care of your child? **[aep_days_work]**
- Q 24. To what extent were you able to go about performing your work or regular planned activities? **[aep_ext_perf_percent]** (0-100%)

Family expenses

Family expenses during exacerbations associated to medications, ED visits, hospitalisations, as well as income loss were recorded at each study contact (phone or visit) by research nurses. The total amount reported during follow up will be summarized for each child as the sum of all amounts reported on the following CRFs:

REDCap, Visit and Phone contact CRF (Section 6):

[phcon_expenses] 6. Have there been any out-of-pocket expenses related to your child's colds or asthma flare-up since the last contact? (Yes/No)

[phcon_expenses_y] 6a. Specify any expenses for (choose all that apply)

1. Prescription drugs Médicaments sur ordonnance;
2. Non-prescription medication/product Médicaments ou produits sans ordonnance;
3. Transport to or parking at medical care facilities Transport ou stationnement aux centres médicaux.

[phcon_insur_cover] 6.2 Did a public or private drug insurance help cover part of the cost of this medication? (Yes/No)

Health care cost

Health care cost, calculated by assigning unit costs to ED visits, hospital admissions, medication use, and physician visits whereas the cost of intervention was determined through drug manufacturer, nursing time, and facility's resources, documented in a random sample of 100 children.

Severity of asthma symptoms

The sum of the daily scores as a measure of the severity of asthma symptoms during exacerbations, completed daily by parents using the validated 17-item, each scored from 1 (best) to 7 (worst), Asthma Flare-Up Diary for Young Children symptoms (ADYC) and standardized over 7 days using the method published in [name] et al. 2016.

Parents are asked to record any asthma symptoms child has experienced during the past 24 hours, the diary should be completed every evening from the first day of cold symptoms until 2 days with no asthma symptoms.

Data source: REDCap3 – written parental report, CRF “Cold and Asthma Flare Up Diary For Young Children (ADYC)”

Q1 - Q7, the Symptoms over last 24 hours:

1 (Never) to 7 (All the time), with “Cannot answer” (coded as 0 (zero)) and should be considered as missing.

Q8 – Q14, the Degree to which each symptom has been a problem observed

1 (Not at all) to 7 (Extremely), with “Cannot answer” (coded as 0 (zero)) and should be considered as missing.

Q15-Q17 the Degree to which the child responded to rescue bronchodilator – special cases:

1 (Not at all) to 7 (Extremely), with “Cannot answer” should be considered as missing or 1, conditional on the response to the question: Has your child taken Ventolin (or blue inhaler) (salbutamol, Bricanyl®, terbutaline but NOT Zenhale)? [adyc_blue_inh] (1:Yes, 0:No)

The logic is:

- If Ventolin was not taken, all 3 questions should be considered as absence of negative symptoms, thus recoded for 1 (Not at all) category;
- If Ventolin was taken, the documented responses for 3 questions should be considered for further score calculation.

Which is in terms of coding:

1. If [adyc_blue_inh] == 0 (No), then three questions: Q15 (Does not respond as well to Ventolin® (or blue inhaler) as usual), Q16 (Does not respond as rapidly to Ventolin® (or blue inhaler) as usual) and Q17 (The effect of Ventolin® (or blue inhaler) does not last as long as usual) are not applicable and should be considered as absence of negative effects, recorded as 1 (Not at all):
 - Q15: [adyc_respondness_vent_deg] = 1;
 - Q16: [adyc_rapidness_vent_deg] = 1;
 - Q17: [adyc_last_vent_deg] = 1
2. If [adyc_blue_inh] == 1 (Yes), then documented values for all 3 questions, Q15, Q16 and Q17 should be used for calculations.

Definition of a valid ADYC day

- At least 9 items out of 17 must be answered, after recording of Questions 15 to 17 in case of no use of bronchodilator (see above); otherwise, the daily score will be set to missing.
- If there are more than 8 missing items (out of 17) on ADYC day 1, then all computations described below will start on ADYC day 2.

Identification of a valid ADYC set (event)

- At least 2 or more consecutive days with a valid ADYC day.

Symptom score calculation

- For each valid ADYC day, the **daily symptom score** will be computed as the mean of all (max of 17) non missing items. The minimum score will therefore be 1 (all non-missing responses

equal 1) and the maximum score will be 7 (if all non-missing responses equal 7).

Cumulative and average symptom score during an episode

- Cumulative episode symptom score = \sum daily ADYC score from the first day with symptom until last day with symptoms, inclusively. Standardized over 7 days value to be reported.
- Average episode symptom score = Cumulative symptom score \div duration of symptoms, units [score/day] (see below) Min = 1, max = 7
This includes ADYC days that did not fulfil the definition of asthma symptom days.

Missing ADYCs - imputation

- If a daily score is missing between the first and the last day with symptoms, the score will be imputed using the last score carried forward.
- The cumulative symptom score will then be computed as the sum of all daily scores between the first and last day with symptoms.

Intensity of use of rescue B2-agonists

Intensity of use of rescue β 2-agonists during asthma exacerbations, defined as:

- Cumulative rescue bronchodilator use: \sum daily number of puffs from the first day until last day of use until last day of use, inclusively. Units [puffs/episode]
- Average rescue bronchodilator score = Cumulative rescue bronchodilator use \div duration of use, units [average puffs/day]

To be reported as a group difference in the mean cumulative use of rescue β 2-agonists per child during exacerbations documented on the validated 'Asthma Flare-up Diary for Young Children' over the 7 months time frame.

A valid diary set was defined as least 2 or more consecutive days with valid reporting of B2-agonist use, with no more than one missing day of recording between the first and last day of reporting. If a daily value is missing between the first and the last day of bronchodilator use, the score will be imputed using the last score carried forward.

- Q: Has your child taken Ventolin (or blue inhaler) (salbutamol, Bricanyl®, terbutaline but NOT Zenhale)? [adyc_blue_inh]
- Q: Which? [adyc_blue_inh_choice]
 - 1 : Ventolin® ou salbutamol
 - 2 : Bricanyl® ou terbutaline
- Q: If Yes, and No. puffs (or nebulles) / 24hrs [adyc_blue_inh_ify] is not missing
 - If 1. ventolin, then dose =number of puffs x 1
 - If 2. bricanyl , then dose = number of puffs x2
 - If number of puffs missing, impute from previous day.

Intensity of use of rescue B2-agonists (sum of daily puffs) = sum of daily rescue b2 (including 0), report as median (25%, 75%)

Parental functional status

Parents' functional status during exacerbation per child as documented on the validated 'Effect of a child's asthma flare-up on parents questionnaire'. Only one parent is surveyed for each flare-up

Documented in REDCap3, CRF Effects of a Young Child's Cold or Asthma Flare-up on Parents (ECAP), completed by parents after each exacerbation: 21 questions.

- A Valid ECAP questionnaire requires a min of 11 questions non-missing
- The **ECAP score** = is the total score was the average of all completed (non missing) items (score range, 1-7).
- **Global parental functional status assessment** = Q 22. Overall, how much did this asthma flare-up affect you? [aep_grav_3] (1 :Not at all – 7 : Extremely, with 8: Cannot answer);

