The number of urgent care events during the 7-month study follow up period will be calculated as the number of times an acute care visit or hospital admission for asthma or asthma-like diagnosis was reported by verbal report of a parent and confirmed by the research coordinators either from the medical records or from parental reports (including the diary) or (ii) written report on diary (with each means of recording considered as a separate outcome). Urgent care events within 7 days of each other will be merged and considered as one event.

Children with at least one acute care visit for asthma, children requiring at least one course of oral corticosteroids for asthma and children with at least one hospitalisation for asthma will also be reported

Treatment intensification at Visit 2 & 3

Treatment intensification (vs. no change or treatment de-intensification) at V2 (3.5 months) and V3 (7 months) time points is reported by the treating physician. Intensification is defined as an increase in the total daily dose of ICS of more than 50 ug/day, the addition of an additional daily preventive drug, or an increase of more than 200 ug/day in the dose of ICS if given pre-emptively at the onset of an exacerbation.

Duration of asthma symptoms

Duration of asthma symptoms for each exacerbation event will be collected through verbal and written parental report (with each means of recording considered as a separate outcome). For each child the average duration of symptoms during exacerbations will be calculated for reported events.

Total duration of β 2-agonist use

Total duration of β 2-agonist use will be collected through verbal and written parental report (with each means of recording considered as a separate outcome). This will be defined as total number of days when β 2-agonist (the rescue bronchodilator - ventolin, bricanyl - blue inhaler) was used during each cold/asthma flare-up.

Number of lost parental workdays

The impact of flare-ups on the number of lost parental workdays as documented through verbal and written parent reports (with each means of recording considered as a separate outcome). This will be summarized as the total number of days that a parent reports that he/she missed work due to a

cold or asthma flare up or to take care of his/her child related to an asthma flare up. Only one parent is surveyed for each flare-up.

Family expenses

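### The written version of lost parental workdays comes from a question that also counts missed non-work activities, so it does not measure the outcome as defined

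*SAP*

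**What the plan says.** Two places in the SAP define the outcome: the secondary outcomes section, under the number of lost parental workdays, and Appendix 2, under lost parental workdays and productivity. Both give the same definition: "This will be summarized as the total number of days that a parent reports that he/she missed work". Both add: "Only one parent is surveyed for each flare-up".

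The secondary outcomes section treats the two reporting routes separately: "The impact of flare-ups on the number of lost parental workdays as documented through verbal and written parent reports (with each means of recording considered" (the sentence goes on to make each route an outcome of its own). Appendix 2 then names the source of each:

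- **Verbal report** (Visit and Phone Contact form, section 7). The opening question is "has any of the child's parents or guardians missed work due to the child's cold or asthma flare-up". The coding note continues "Up to Q 7.1.1 and 7.2.1 and 7.3.1 etc". The wording of these sub-items is not shown.
- **Written report** (ECAP questionnaire, question 23, variable aep_days_work). The question is "How many days of work or regular planned activities did you miss because you had to take care of your child".

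Under secondary outcome analyses, lost parental workdays is listed among the counts to be compared by arm with a Poisson or negative binomial model adjusted for site.

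**The concern.** The definition and the written item do not describe the same quantity. The definition is limited to missed work. Question 23 asks about work or other planned activities and returns one number. A programmer who follows Appendix 2 exactly will therefore produce a variable that includes days on which no work was lost, and the SAP's label will carry it into the results as lost workdays.

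What is at stake is what the written result can be said to show. A mean or rate ratio from question 23 supports a statement about disruption to the responding parent's work or usual activities. It does not support a statement about work loss. The Appendix 2 heading joins workdays with productivity, which makes a reading in terms of work loss more likely. Because the SAP puts both routes under one definition, a reader could also take a difference between the verbal and written results for reporting error, when part of it may come from the different content of the questions.

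**Working it through.** The SAP gives no figure for lost workdays, so there is none to reproduce. The check sets the definition against each item.

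| | Definition | Written item (ECAP question 23) | Verbal item (question 7, opening question) |
|---|---|---|---|
| What is missed | Work | Work or other planned activities, in one number | Work |
| Whose days | A parent's own (he/she) | The responding parent's | Any parent or guardian; unit of the sub-items not shown |

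**Written item.** Write W for days of missed work and A for days on which only non-work activities were missed. Question 23 records

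Q23 = W + A,

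and the definition asks for W. The excess over the defined outcome is Q23 − W = A, which is zero or positive. Recovering W would need a rule that separates the two parts or a record of A. Appendix 2 gives neither. The next question listed, question 24, asks for a percentage of work or planned activities performed on the same combined basis, so it does not help. As an illustration, a parent without paid work who gives up 3 days of planned activities has W = 0 and A = 3. The written outcome records 3 and the defined outcome is 0. The share W/Q23 can lie anywhere from 0 to 1, and the SAP has no data to narrow that range.

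**Effect on the comparison of arms.** Let subscripts 1 and 0 denote the mean per child on vitamin D and on placebo. The simple ratio of means from question 23 is

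(W1 + A1)/(W0 + A0) = p × (W1/W0) + (1 − p) × (A1/A0), with p = W0/(W0 + A0).

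It is a weighted average of the ratio for work and the ratio for other activities. If the two ratios are equal, the relative effect is unchanged and only the mean level is too high. If they differ, the result answers a question about the mixture. The SAP gives no reason to expect either case, so no direction of error can be stated.

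**Verbal item.** The opening question refers to missed work only, so its content matches the definition. Its scope, any parent or guardian, is wider than the he/she of the definition. Whether the sub-items record days per guardian, per episode or in some other unit cannot be read from the SAP.

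**The case against.** The strongest reply has four parts.

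1. *The two routes are analysed separately.* This stands as far as it goes: the content of question 23 cannot affect the verbal result. It does not correct the label on the written result.
2. *The wider scope is disclosed, because Appendix 2 reproduces the question in full.* That helps a reader of the appendix. The definition above it still says missed work, and the outcome name carries that meaning into the results.
3. *The SAP does not assign question 23 to any cost calculation.* This stands. Health care cost is built from visits, admissions, medication and the cost of the intervention, and family expenses come from the study contacts. Misuse for productivity is a risk of interpretation and is not planned in the SAP.
4. *Both arms answer the same questions, so no bias is shown.* This also stands, and none is claimed.

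A reader might go further and infer that neither item measures lost workdays, or that the verbal total adds up days over several guardians in conflict with the one-parent rule. The SAP does not support this. The verbal question is about missed work. The sentence on surveying one parent can mean that one person answers for the household. The sub-items are cited by number only, and elsewhere the same form repeats question blocks for further acute-care visits (questions 3 and 4), so repeated numbering does not show that each repeat is a guardian. What is left on the verbal side is a counting unit that the SAP does not state.

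**Conclusion.** The point holds for the written version only. As coded from ECAP question 23, it counts missed work and other missed planned activities together and does not measure the outcome as the SAP defines it. This follows from the text and needs no assumption about the data. The size of the excess cannot be derived: it is zero if every reported day was a workday and the whole count if none was. No bias between arms is shown.

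The verbal version measures missed work. Its definition needs a clarifying clause on whose days count, but the SAP gives no ground for calling its total wrong.

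This is a minor point about one of many secondary outcomes. It is worth making because it changes what the written result may be said to show.

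**What to change.** 1. Rename the written outcome, in both the secondary outcomes section and Appendix 2, so that it covers days of work or other planned activities missed by the responding parent. Carry that name into the tables, and make no statement about lost workdays or productivity from it.
2. Keep verbal question 7 as the lost-workdays outcome.
3. For question 7, check the sub-items on the form and align the he/she wording in both sections with what they record, whether that is the respondent's days only or those of all guardians. The form should settle this. Summing over guardians should not be assumed.

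The cost is a change of SAP wording and table labels. No new data are needed and the models stay as planned. The downside is that one of the two outcomes loses the workdays name.

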Adherence to the protocol will be defined as participants having no major protocol deviations, as specified in the protocol's list of major deviations (see 'per-protocol sample'). Specifically, participants must have received at least 50% of the correct bolus dose under nursing supervision in the clinic and consistently taken the daily supplement as prescribed. In the pilot trials, adherence to the bolus dose was ensured by nursing administration in the clinic, and median adherence to daily supplement administration was over 92%, based on the weighing of returned bottles.

Major protocol deviations that will be reported and may result in changes to the analysis include instances where the wrong study drug was administered, the study bolus was not administered or less than 50% was swallowed, daily supplement bottles were not provided or collected, patients missed the daily supplement for 40 or more days, unblinding of study treatment occurred, ineligible patients were randomized, or bolus administration occurred without necessary lab results or despite abnormal results in patients with low calcium intake. Any deviation impacting patient rights, safety, welfare, or the integrity of the study data will also be considered.

Handling of missing values and other data conventions

A nested loop of imputation of missing values with regression (to adjust for baseline variables) and bootstrapping (to estimate uncertainty) will be used. This approach reduces bias, ensures imputed values reflect baseline differences, and provides robust estimates of variability and confidence intervals, thereby minimizing the impact of missing data and ensuring robust and reliable results.

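### The one-missing-day cap on rescue β2-agonist diary sets drops long episodes preferentially, and ADYC carry-forward has no gap limit

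*SAP*

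**What the plan says.** Two outcomes from the same parent diary are given different gap rules in Appendix 2.

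- **Rescue β2-agonist use** (sections on total duration and on intensity of use). "A valid diary set was defined as least 2 or more consecutive days with valid reporting of B2-agonist use", and the set must also come "with no more than one missing day of recording between the first and last day of reporting". A permitted missing day takes the previous value. Sets with two or more missing days fail the definition, and no other handling is given for them. The duration section closes by defining duration as the time elapsed from the first to the last day of use.
- **ADYC severity.** A day with fewer than 9 of 17 items answered does not count: "otherwise, the daily score will be set to missing". A set is valid on one condition: "At least 2 or more consecutive days with a valid ADYC day". For any day without a score inside the symptom period, the rule is that "the score will be imputed using the last score carried forward". No maximum gap is stated. Imputed days enter the cumulative score, which is "computed as the sum of all daily scores between the first and last day with symptoms".

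The main text, under handling of missing values, plans something else: "A nested loop of imputation of missing values with regression", with bootstrapping for uncertainty, and multiple imputation is named for loss to follow-up. It does not mention the diary rules, and Appendix 2 does not mention the main-text method. No sensitivity analysis of the diary rules is planned.

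**The concern.** A cap of one missing day is lenient for a 5-day episode and strict for a 3-week one, because a longer episode has more days on which an entry can be missed. Whether an episode enters the analysis then depends on its length, and length is one of the outcomes; cumulative puffs rise with it. If vitamin D shortens rescue use, the control arm has more long episodes and loses more of them, so the contrast shrinks without any difference in diary-keeping between arms. For duration the exclusion also gains nothing, since elapsed time is known once the first and last day of use are recorded.

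The ADYC rule has the opposite weakness. Two consecutive valid days and one later symptom day are enough, and every day between is filled with the earlier score although a later score is on record. An episode with several missed days can therefore be invalid for rescue use and heavily imputed for severity.

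**Working it through.** The SAP states no figure on this point, so there is none to reproduce. The rules come from Appendix 2. The rate of missed days, the episode lengths and the course of the score are not in the document and are assumed below.

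**1. Chance that a rescue-use set is kept.** Take a set of L days with the first and last day recorded and each of the L − 2 interior days missed independently with probability q. Then

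P(kept) = (1 − q)^(L−2) + (L − 2) q (1 − q)^(L−3).

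Example, L = 14, q = 0.10: 0.9^12 + 12 × 0.1 × 0.9^11 = 0.282 + 0.377 = 0.659.

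| Missed per day | 5 days | 7 days | 10 days | 14 days | 21 days |
|---|---|---|---|---|---|
| 5% | 99.3% | 97.7% | 94.3% | 88.2% | 75.5% |
| 10% | 97.2% | 91.9% | 81.3% | 65.9% | 42.0% |
| 20% | 89.6% | 73.7% | 50.3% | 27.5% | 8.3% |

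With an assumed spread of lengths from 3 to 21 days (mean 8.67), the share of sets lost is 4.8%, 14.9% and 37.8% at these three rates. The mean length of the sets kept falls to 8.52, 8.21 and 7.41 days.

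**2. Effect on a between-arm ratio, by hand.** Let half the control episodes last 4 days and half 12 (mean 8), and let treatment shorten each by a quarter, to 3 and 9 days (mean 6). The true ratio is 6/8 = 0.75. Use the same q = 0.10 in both arms.

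- Chance kept: 4 days 0.990; 12 days 0.9^10 + 10 × 0.1 × 0.9^9 = 0.736; 3 days 1.000; 9 days 0.9^7 + 7 × 0.1 × 0.9^6 = 0.850.
- Control mean among kept sets: (4 × 0.990 + 12 × 0.736)/(0.990 + 0.736) = 7.41.
- Treated mean among kept sets: (3 × 1.000 + 9 × 0.850)/(1.000 + 0.850) = 5.76.
- Observed ratio: 5.76/7.41 = 0.78.

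Simulation with gamma-distributed durations (means 8 and 6, equal missingness) gives about 0.78 for shape 4 and 0.80 for shape 2 at 10% missed, and 0.76 to 0.77 at 5%. A wider spread (shape 1) gives about 0.84 at 10%. The second decimal also moves with how durations are rounded to whole days.

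**3. ADYC carry-forward.** Take a 10-day course rising from 2.0 to 4.5 on day 3 and falling linearly to 1.5 on day 10; the true sum is 29.25.

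| Days missing | Error in the sum |
|---|---|
| 5 | +1.5% |
| 4–5 | +4.4% |
| 4–7 | +14.7% |
| 2 | −4.3% |
| 2–3 | −12.8% |
| 2–5 | −25.5% |

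The sign follows the phase in which the gap falls. With interior days missed at random the errors nearly cancel on average: +0.01% at 10% missed and −0.07% at 20%. A second assumed course (3.0, 4.0, 3.6, 3.2, 2.8, 2.4, 2.1, 1.8, 1.5; sum 24.4), which spends more of its days in decline, gives +0.5% and +1.2%.

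Error in a single episode does not cancel. At 10% missed, the root-mean-square error of the sum is 2.0% with carry-forward against about 1% with linear interpolation in the 9-day course, and 2.6% against 1.25% in the 10-day course.

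**The case against.** Four points on the other side deserve weight.

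- **The miss rate is unknown.** Parents received text and email reminders. At 5% missed, a 14-day set is still kept 88% of the time and the ratio barely moves. This stands: the direction is certain, the size is not. A reader might infer that the cap removes long episodes outright. It does not; it removes them preferentially.
- **Carry-forward may be nearly harmless.** A reader might infer that it systematically masks recovery, for instance because losing days 4 to 9 of the 10-day course overstates the sum by 31%. That takes six consecutive missing days just after the peak. The SAP gives no gap frequencies that would make this typical, gaps during worsening err the other way, and random gaps nearly cancel. Imputation also stops at the last recorded symptom day and does not enter diary duration of symptoms, which is elapsed time. Nothing in the document shows that the ADYC rule shrinks a treatment effect.
- **Interpolation is a convention, not the truth.** It clips a missed peak: if day 3 of the 10-day course is lost, it gives (3.25 + 4.07)/2 = 3.66 instead of 4.5, an error of −0.84/29.25 = −2.9%, against −4.3% with carry-forward. It is closer, not exact. The published method cited for 7-day standardisation was not available and may contain its own gap rule.
- **Duration is also described as a number of days of use.** On that reading an interior gap does leave something unknown. But the section's closing definition is elapsed time, and on either reading filling the gap loses less than discarding the episode.

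Verbally reported duration of β2-agonist use is a separate outcome to which the cap does not apply. That limits the damage but does not repair the diary outcome.

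**Conclusion.** The point holds for the rescue-use cap and, in a weaker form, for ADYC scoring.

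The cap makes inclusion depend on episode length and so attenuates a true difference in diary duration even with identical missingness in both arms: from 0.75 to about 0.78–0.80 at 10% missed and 0.76–0.77 at 5%. This rests on independent misses, recorded first and last days, and the assumed spread of durations; 0.75 is an illustration, not an effect that the SAP predicts for this outcome. Cumulative puffs are exposed to the same selection.

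Unlimited ADYC carry-forward is mainly a matter of precision and of consistency with the main-text imputation plan. It roughly doubles the error per episode relative to interpolation, with little average bias under random gaps. A bias between arms in ADYC scores would need gaps or symptom courses that differ by arm in a particular way, which the document cannot show.

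Only secondary diary outcomes are touched: diary duration and intensity of rescue use, and symptom severity. The primary count of OCS-treated exacerbations is not. The change should be made, but it does not threaten the trial's main conclusion.

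**What to change.** - **Diary duration of rescue use:** drop the missing-day cap and use every set with a recorded first and last day of use. State once that duration means elapsed time.
- **Cumulative puffs and ADYC scores:** do not exclude on an absolute count of missing days. Interpolate short interior gaps linearly between the flanking recorded days, with the maximum length fixed in advance (two consecutive days would be a workable convention). Handle longer gaps with the multiple imputation already planned in the main text. Do not sum recorded days only, which would understate the total.
- **Reporting:** give by arm the number of sets excluded, the number of days imputed and the distribution of gap lengths.
- **Sensitivity analysis:** keep the present cap and carry-forward scoring, so that results stay comparable with earlier use of the diary.
- **Consistency:** add a sentence to the missing-data section saying which rule governs diary days.

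The cost is SAP wording and some recoding, settled without sight of treatment allocation, and a departure from the instrument's customary scoring if that used carry-forward. No new data are needed.
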